8 RESEARCH METHODS

8.1 Study Design

The UNITY Global Registry is designed as a comparative cohort study using longitudinal serial surveys implemented through a web/mobile application-based technology to encourage participation and facilitate rapid responses during this pandemic. The study population comprises adult male and female HCWs working in healthcare facilities (e.g., acute care hospital) or in a community healthcare setting (e.g., clinic) with ongoing and continuous exposure to confirmed or clinically diagnosed COVID-19 patients. Countries and healthcare facilities will be selected based on the availability of potential prophylactic treatments to prevent workplace infection from SARS-CoV-2. The association of potential prophylactic treatments will be measured using the WHO Ordinal Scale of Clinical Improvement.⁹

Individuals with workplace exposure to confirmed or clinically diagnosed COVID-19 patients prior to enrollment, or anticipated within 30 days after enrollment, will be eligible to participate. COVID-19 exposure is defined as per WHO classification.⁹ The date of the HCW's first known exposure to a confirmed or clinically diagnosed case of COVID-19 is referred to as the "Index Date" (see Figure 2). Healthcare worker volunteers are ineligible if they had COVID-19 or symptoms highly suggestive of COVID-19 before the Index Date. However, at the time of enrollment, HCWs can be either SARS-CoV-2 positive (symptomatic or asymptomatic) or SARS-CoV-2 negative.

Healthcare workers will be identified for participation via a central contact at participating healthcare facilities and directed to a website/mobile application allowing them to electronically consent (in parallel, paper consents may be used, as per local requirements) and answer questions that would help assess their eligibility to participate. Information on potential prophylactic treatments used by HCWs will also be collected. The website/mobile application will prompt participants to provide entry-level information such as, demographics, underlying conditions, and exposure to COVID-19 patients.

[figure not shown]
Healthcare workers will be expected to provide information on a weekly basis, for 12 weeks after enrollment. In case HCWs stop responding (after due diligence reminders), their secondary contacts (identified by the HCW, may be next of kin or other individuals informed of HCW's health status) will be approached. In case of conflicts, responses by HCWs will take precedence.

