Enrollment will be monitored and potentially capped to ensure that the study enrolls an aggregate of at least 75% of HCWs who are taking a potential prophylactic therapy.

For details on the information collected and the overall study design, refer to [Table 1](#), [Table 2](#), [Figure 1](#), and [Figure 2](#), respectively.

This is a comparative observational cohort study; therefore, no preventive interventions, visits or laboratory tests are mandated. Dosing and duration of potential prophylactic treatment is at the discretion of the institution and/or healthcare provider, in accordance with regular local practice. However, serology testing for SARS-CoV-2 antibodies may be offered to approximately 50% of participating HCWs per country, at enrollment (ranging from baseline up to Week 4 [African countries] and Week 8 [Pakistan]) and at the last follow-up (i.e. at Week 12).

Figure 1 Study Schematic - High-level

HCW: Healthcare Worker

Figure 2 Study Schematic – Healthcare Worker Flow

[figure not shown]

Table 1 Schedule of Assessments – Healthcare Worker Flow

Variable domain	At Enrollment		Weekly follow-up (until Week 12) ^c	
	HCW	HCW	Secondary Contact	
Inclusion/eligibility criteria (screening questions/index date)	X	-	-	-
Electronic/paper (if applicable) consent	X	-	-	-
Demographics	X	-	-	-
Underlying conditions	X	-	-	-
Job characteristics	X	-	-	-
BCG vaccination history	X	-	-	-
Household history (COVID-19)	X	X	-	-
COVID-19 exposure	X	X	-	-
Prophylactic treatments	X	X	-	-
Concomitant medications	X	X	-	-
COVID-19 vaccination ^e	X	X	-	-
PPE	X	X	-	-
COVID-19 symptoms	X	X	-	-
SARS-CoV-2 testing	X	X	-	-
Serology testing ^f	X	X ^b	-	-
WHO Ordinal Scale for Clinical Improvement ^d	X	X	-	X ^a

BCG: Bacillus Calmette–Guérin; CoV: Coronavirus; HCW: Healthcare worker; PPE: Personal Protective Equipment; SARS: Severe acute respiratory syndrome; WHO: World Health Organization.

^a: In case HCWs stop responding (after due diligence reminders), their secondary contacts will be approached. In case of conflicts, responses by HCWs will be considered.

^b: Testing to be requested at last (Week 12) follow-up.

^c: Or, time since last follow-up, whichever is greater.

^d: Adapted, abbreviated version.

^e: From the time the questions on vaccination go live in the web application online survey, baseline vaccination information will only be collected for newly enrolled HCW and for HCWs who did not complete the survey prior to the addition of vaccination questions.

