8.3 Variables

The sections below include outcomes, treatment exposure and PPE use, COVID-19 exposure, COVID-19 vaccinations, and other variables to be measured and accounted for in the study analyses. Refer to [Appendix 2](#) for further details.

8.3.1 *Clinical Outcomes Variables*

- WHO Ordinal Scale for Clinical Improvement of COVID-19 (adapted, abbreviated version)
 - SARS-CoV-2 (uninfected/infected)
 - Ambulatory status (limitation/no limitation of activities)
 - Hospitalized with no intensive care unit (ICU) or mechanical ventilation (mild)
 - Hospitalized with ICU and/or mechanical ventilation (severe)
 - Death

8.3.2 *Prophylactic Treatment (Treatment Exposure)*

- Types, intake frequency, and doses of prophylactic treatments
 - Treatment name
 - Date started
 - Date stopped
 - Dose (intake)
 - Duration of treatment
 - Dose frequency and dosing interval
 - Status (stopped/ongoing)
 - Reason for stopping (not available/side effects/expense/other)
 - Number of missed doses and reason (not available/side effects/expense/other)

8.3.3 *History of Exposure to COVID-19 Patients*

- At enrollment
 - Self-reported ongoing and recurrent exposure (yes/no)
 - WHO exposure definition (3 questions) (yes/no)
 - Direct patient care (yes/no)
 - Face-to-face contact (yes/no)
 - Present during aerosol-generating procedure (yes/no)
- Weekly follow-up
 - Self-reported ongoing and recurrent exposure (yes/no)
 - WHO exposure definition (3 questions) for past week

- Days worked past week
- Number of COVID-19 cases exposed to in the past week

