- Antiparasitics (yes/no). If yes, please specify.
 - Ivermectin (yes/no)
 - Other antiparasitics.
- Antiretrovirals for Human Immunodeficiency Virus (HIV) (yes/no). If yes, please specify.
 - Lopinavir
 - Ritonavir
 - Tenofovir
 - Nelfinavir
 - Other antiretrovirals
- Antivirals (yes/no). If yes, please specify.
 - Oseltamivir
 - Favipiravir
 - Arbidol
 - Anti-hepatitis C treatments
 - Remdesivir
 - Other antivirals
- Medication for high blood pressure and cardiovascular disease (yes/no). If yes, please specify.
 - Angiotensin-converting enzyme (ACE) inhibitor (e.g., lisinopril, enalapril)
 - Angiotensin II receptor blockers (ARB) inhibitor (e.g., losartan, irbesartan)
 - Other anti-hypertensive for high blood pressure
 - Other medicine for high blood pressure and cardiovascular disease (e.g., antiarrhythmics, inotropes, chronotropes)
- Nonsteroidal Anti-inflammatory Drugs (NSAIDs) e.g., Aspirin, Ibuprofen, Indomethacin, Celecoxib, Diclofenac (yes/no). If yes, please specify.
- Botanicals (yes/no)
 - Artemisia teas (COVID Organics)
- Immunocompromising drugs (yes/no). If yes, please specify.
 - Corticosteroids
 - Cancer chemotherapy

- Cyclosporine
- Drugs for autoimmune conditions such as lupus or rheumatoid arthritis, Crohn's disease
- Changes in concomitant medications.
- COVID-19 vaccinations
 - Convidicea (Ad5-nCoV)
 - CoronaVac (Sinovac)
 - Covaxin (BBV152)
 - EpiVacCorona (Vector Institute)
 - Janssen Pharmaceuticals (Johnson & Johnson) (Ad26.COV2.S)
 - Moderna COVID-19 Vaccine
 - Novavax (NVX-CoV2373)
 - Oxford-AstraZeneca COVID-19 Vaccine
 - Pfizer-BioNTech COVID-19 Vaccine
 - Sinopharm BBIBP-CorV
 - Sputnik V COVID-19 Vaccine
 - Other (to be specified)

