Pneumonia	X	X	-
Nausea or vomiting	X	X	-
Headache or migraine	X	X	-
Abdominal pain (pain in tummy)	X	X	-
Asthenia (weakness or loss of strength)	X	X	-
Arthralgia (joint pain)	X	X	-
Anosmia (loss of smell)	X	X	-
Ageusia (loss of taste)	X	X	-
Blue coloring in toes	X	X	-
Diarrhea (two or more looser-than-normal stools in 24 hours)	X	X	-
SARS-CoV-2 testing			
Tested? (yes/no)	X	X	-
Type of test	X	X	-
PCR (positive/negative)	X	X	-
Antigen test (positive/negative)	X	X	-
Serology (IgG and/ or IgM, positive/negative or titer)	X	X	-
Date of test	X	X	-
Serology testing	X	X	-
Household history (COVID-19)			
Number of household contacts	X	X	-
Additional household member(s) exposed to COVID-19 (yes/no) If yes, how many?	X	X	-
Additional household member(s) with symptoms consistent with COVID-19 (yes/no) If yes, how many?	X	X	-
Additional household member(s) diagnosed with COVID-19 (yes/no) If yes, how many?	X	X	-
Underlying conditions and key morbidities			
Chronic lung disease	X	-	-
Diabetes mellitus	X	-	-
Cardiovascular (heart) disease	X	-	-
Chronic renal (kidney) disease	X	-	-
Chronic liver disease	X	-	-
Immunocompromised condition (HIV/AIDS, organ transplant, other)	X	-	-
Tuberculosis	X	-	-
Neurologic/neurodevelopmental	X	-	-
Hypertension (high blood pressure)	X	-	-
History of stroke	X	-	-
Other chronic diseases	X	-	-
If female, currently pregnant	X	-	-
If female, currently breastfeeding/lactating	X	-	-
Job characteristics			
Type of healthcare work	X	-	-

Primary work location (ED, ICU, Medical floor)	X	X	-
Number of hours with patients	X	X	-
Concomitant medications (other than for COVID-19)			
Antibiotics (yes/no)	X	X	-
Antimalarials (yes/no)	X	X	-
Antiparasitics (yes/no)	X	X	-
Antiretrovirals for HIV (yes/no)	X	X	-
Antivirals (yes/no)	X	X	-
Medication for high blood pressure and cardiovascular disease (yes/no)	X	X	-
Nonsteroidal Anti-inflammatory Drugs (NSAIDs) (yes/no)	X	X	-
Botanicals (yes/no)	X	X	-
Immunocompromising drugs (yes/no)	X	X	-
COVID-19 vaccine (to be selected as applicable)			
Convidicea (Ad5-nCoV)	X	X	
CoronaVac (Sinovac)	X	X	
Covaxin (BBV152)	X	X	
EpiVacCorona (Vector Institute)	X	X	
Janssen Pharmaceuticals (Johnson & Johnson) (Ad26.COV2.S)	X	X	
Moderna COVID-19 Vaccine	X	X	
Novavax (NVX-CoV2373)	X	X	
Oxford-AstraZeneca COVID-19 Vaccine	X	X	
Pfizer-BioNTech COVID-19 Vaccine	X	X	
Sinopharm BBIBP-CorV	X	X	
Sputnik V COVID-19 Vaccine	X	X	
Other (please specify)	X	X	

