6.1 Overview.....	17
6.2 Missing values.....	18
6.2.1 Missing values for non-outcome variables	18
6.2.2 Missing values for outcomes.....	18
6.3 Descriptive analyses.....	18

6.3.1	Facility characteristics.....	19
6.3.2	Demographic characteristics.....	19
6.3.3	Household characteristics.....	20
6.3.4	Exposure to COVID-19 patients.....	20
6.3.5	Medical history.....	21
6.3.6	Medications for non-COVID-19 related purposes.....	22
6.3.7	Prophylactic medications.....	23
6.3.8	PPE usage	24
6.3.9	COVID-19 symptoms.....	25
6.4	Primary analysis	26
6.4.1	Frailty model: mixed effect Cox regression	26
	Table 5.4.1.....	26
6.5	Secondary analysis	27
6.6	Subgroup analyses	28
6.7	Sensitivity analyses	28
7	Minimization of study bias.....	30
7.1	Selection bias	30
7.2	Survival bias	30
7.3	Recall bias.....	30
7.4	Information bias.....	30
7.5	Indication bias.....	30
7.6	Protopathic bias	31
8	References	31
9	Appendix.....	32
9.1	Shell tables.....	33
	Table 8.2.1 COVID-19 exposure status among all screened healthcare workers.....	33
	Table 8.2.2 Primary and Secondary Outcomes at baseline and follow-up among the overall population	34
Table 8.2.3	Static Variables by COVID-19 indication	35
Table 8.2.4	Household characteristics at baseline by COVID-19 indication.....	37
Table 8.2.5	COVID-19 exposure at baseline by COVID-19 indication	39
Table 8.2.6	Comorbidities at baseline by COVID-19 indication.....	40

Table 8.2.7 Concomitant medications at baseline by COVID-19 indication.....	41
Table 8.2.8 Prophylaxis use.....	43
Table 8.2.9 PPE usage at baseline.....	44

1 Introduction

The purpose of this statistical analysis plan (SAP) is to provide an analytic framework for the study “International Registry of Healthcare Workers Exposed to COVID-19 Patients (UNITY Global)”. This SAP addresses the statistical analyses that will be carried out in support of the protocol objectives. This analysis plan is based on the protocol version 1.0 of the study dated 08 June 2020.

2 Objectives of the study

This is an international registry of HCWs exposed to SARS-CoV-2 while caring for confirmed or clinically diagnosed COVID-19 patients. The aim of this registry is to generate real-world evidence in HCWs to potentially inform recommendations and policies on prevention measures, including prophylactic use of potential drug therapies in HCWs.

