6.4 Primary analysis

6.4.1 Frailty model: mixed effect Cox regression

For the time to COVID-19 infection outcome, both crude and adjusted hazards ratios will be estimated for time to COVID-19 infection with respect to prophylaxis use. The primary objective of this analysis is to assess the association between prophylactic treatments and the reduced risk of SARS-CoV-2 infection in HCWs caring for COVID-19 patients. A mixed effect Cox regression model (ie. frailty model) will be used to estimate adjusted hazard ratios. This method will allow the utilization of both the repeated measures gathered from each HCWs surveys, as well as the incorporation of time-varying covariates of interest such as PPE usage and COVID-19 exposure. Each subject will be included as a random effect. Both time-fixed and time-varying covariates will be included in the model. Covariates will be assessed using a univariate model, any covariates with a p-value less than 0.20 will be included in a multivariate model. A backward stepwise process will then be completed, where the covariates with largest p-value are removed one at a time until all covariates that remain are significant at the 0.10 level. The time-fixed covariates, healthcare facility and country will be included in the model regardless of their significance level. Including the healthcare facility and country covariates will make each healthcare worker's COVID-19 outcome conditionally independent on the background COVID-19 incidence occurring within each subject's healthcare facility and country. A list of additional covariates to be considered can be found in Table 5.4.1. For each subject in the control group, the index date (ie. time of first known exposure to COVID-19 patients) will be used as time zero. For HCWs that are treated with prophylaxis at any time their index date will be 7 days after initiation of treatment. Having an index date near treatment initiation will prevent the introduction of survivorship bias into the analysis.

Table 5.4.1 Model Covariates

Time-fixed/Time-varying Covariate	Covariate Name
Time-fixed Covariates	Healthcare facility, Country, Age, Biological Gender, BMI, Smoking status, Ethnicity, Blood type, Primary work location, Type of healthcare worker, Medical history

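### The primary Cox model has no calendar-time or vaccination term, and SAP 6.4.1 credits time-fixed facility and country terms with a protection against background incidence that they cannot give

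*SAP*

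**What the plan says.** **Forced terms.** SAP 6.4.1 keeps facility and country in the primary mixed-effects Cox model whatever their p-values, and itself classes them as time-fixed. It says that including them makes each worker's "outcome conditionally independent on the background COVID-19 incidence occurring within each" person's facility and country.

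**Other covariates.** Table 5.4.1 lists further time-fixed items and 11 time-varying ones: three on the household, four on patient contact and four on PPE. None is a calendar date, a calendar period or local incidence. All must pass a univariate screen (p<0.20) and backward elimination to 0.10. Where covariates are highly correlated, only one is kept.

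**Clock.** Time zero is first known exposure for controls. For anyone who ever takes prophylaxis it is 7 days after starting.

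**Vaccination.** Protocol v1.1 section 8.3 names "COVID-19 vaccinations, and other variables to be measured and accounted for in the study analyses". Section 8.3.5 files "COVID-19 vaccinations" under other covariates, by product and without dates, and Appendix 2 collects them at enrolment and weekly. Under Table 1 footnote e, "baseline vaccination information will only be collected for newly enrolled HCW" and for workers who had not completed the survey before the questions were added. The SAP introduction states: "This analysis plan is based on the protocol version 1.0 of the study dated 08 June 2020". Vaccination is absent from SAP 3.6.5, from Table 5.4.1 and from the propensity-score covariates in 6.3.

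**Other analyses.** SAP 6.6 and 6.7 use neither calendar period nor vaccination. Time from index date to entry is a duration, not a date. SAP 7.1 and 7.5 cite inverse probability weighting in a section 5.4.2, but section 5 is the sample size and 6.4 contains only 6.4.1.

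**The concern.** A time-fixed site term can hold constant only what is constant at that site. Epidemic waves are not. Because the clock starts at a personal date, two workers at the same facility and the same follow-up time can be in different calendar months, one in a wave and one outside it. The subject random effect is also constant over time and does not help.

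The design makes a link between use and calendar date plausible, though it does not prove one. Enrolment may be capped by prophylaxis status (protocol 8.2.3), it is open-ended, and lack of availability is a listed reason for stopping treatment. Vaccination is a second possible confounder if uptake differs between users and non-users.

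At stake are the primary hazard ratio, which is meant to inform policy on prophylaxis, and the time-to-event secondary analyses that copy its model (SAP 6.5).

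**Working it through.** **1. The plan's own figure.** SAP section 5 gives N = 10,000, 20% unexposed, 10% risk in the unexposed and RR 0.78; SAP 6.1 gives two-sided 5%. Events = 2,000 × 0.10 + 8,000 × 0.078 = 824. Schoenfeld power = Φ(|ln 0.78| × √(824 × 0.2 × 0.8) − 1.96) = Φ(2.853 − 1.960) = 81.4%, close to the stated 80%. The sample size is not in dispute. The implied standard error (SE) of the log hazard ratio (HR) is 1/√131.84 = 0.087.

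**2. The sentence.** Write the hazard at facility f on calendar date c as λ_f × g_f(c). The facility term estimates λ_f. The wave g_f(c) stays, with c equal to the personal time-zero date plus follow-up time. The claimed independence therefore fails whenever g_f varies.

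**3. Static size, true HR 1.** The documents give no wave size, vaccine effect or coverage, so all inputs from here on are assumptions.
- Wave: apparent HR = [1 + p_u(W − 1)] / [1 + p_n(W − 1)], where p_u and p_n are the shares of users' and non-users' person-time in a W-fold wave. With 40% and 60%: W = 2 gives 1.4/1.6 = 0.875; W = 3 gives 1.8/2.2 = 0.82; W = 5 gives 2.6/3.4 = 0.765. Shares reversed: 1.14, 1.22, 1.31.
- Vaccination: apparent HR = (1 − VE·v_u) / (1 − VE·v_n), with coverage v_u = 40% in users and v_n = 20% in non-users. Effectiveness (VE) of 50%, 70% and 90% gives 0.80/0.90 = 0.89, 0.72/0.86 = 0.84 and 0.64/0.82 = 0.78. Coverage reversed: 1.125, 1.19, 1.28.

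These hold the full gap throughout follow-up and are upper-end illustrations.

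**4. Wave simulation with staggered follow-up, true HR 1.** 10,000 workers, 9 countries × 5 facilities, about 80% users, a 120-day wave, 200 replicates (Monte Carlo SE at most 0.007). The SAP model is approximated by facility and follow-up-week terms; brackets add weekly contacts and household cases, always kept.

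| Use in wave vs outside | Hazard ×2 | Hazard ×4 |
|---|---|---|
| 70% vs 85% | 0.94 (0.94) | 0.90 (0.92) |
| 90% vs 75% | 1.05 (1.05) | 1.12 (1.09) |
| 75% vs 82% | 0.98 (0.98) | 0.96 (0.97) |
| no difference | 1.01 (1.01) | 1.01 (1.01) |

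Calendar-date Cox stratified by facility gave 0.99-1.01 in these cases; facility plus country-by-month gave 0.99-1.02.

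**5. A separate simulation under stronger assumptions.** 40 facilities, a 90-day wave of 2-, 3- or 5-fold, 12-week follow-up, 30 runs each. Use of 90% near the wave vs 75% gave 1.11, 1.19 and 1.28; 65% vs 84% gave 0.88, 0.85 and 0.76; no link gave 0.99-1.01. Adding 14-day calendar start blocks to the strata gave 0.98-1.03 throughout.

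**6. Vaccination with gradual rollout, true HR 1.** Final coverage 60% of users vs 40% of non-users unless stated. The middle column adds status (unvaccinated, vaccinated, unknown) to the calendar model, with no answer carried back.

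| Scenario | SAP model | Three-level status |
|---|---|---|
| VE 80% | 0.89-0.91 | 0.95-0.97 |
| VE 50% | 0.95 | 0.98 |
| Coverage reversed | 1.11 | 1.03 |
| 20% vs 10% | 0.96 | 0.99 |

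Status thus removes about half to three quarters of the log bias; calendar terms alone did not change it. Starting follow-up at the first vaccination answer gave 1.00-1.02.

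**7. Consequence.** With SE 0.087 and true HR 1, a bias to 0.94, 0.90 or 0.85 gives p<0.05 in about 11%, 23% or 47% of studies instead of 5%.

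**The case against.** - *Contacts and household cases already follow the wave.* In part. Keeping them moved 0.90 only to 0.92 and 1.12 only to 1.09, and the selection or correlation rules may drop them.
- *The SAP has other safeguards.* SAP 6.3 tabulates weekly incidence by facility, compares it by prophylaxis use and displays propensity scores over weeks; 6.3.7 plots use by survey date. Protocol 8.7.4 leaves weighting and marginal structural methods open. The displays could reveal a shift in use, but they do not adjust the primary hazard ratio, and the weighting is not specified in the SAP.
- *The sizes are assumed, and the simulated model is not the SAP's.* This stands. The simulations had no subject random effect, no p-value selection and no PPE terms, and results depend strongly on the scenario.
- *Facility strata have a cost in SAP 6.5.* This stands. That section removes each covariate from the final primary model and applies a likelihood ratio test. Strata leave no facility or country coefficient to test.
- *Vaccination's role is not settled.* This stands in part. Amendment 1 added it to update information on prophylactic treatments, and earlier prophylaxis could influence uptake. The SAP should state its role, but leaving it out of every analysis does not settle that.

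A reader might infer that protocol 8.3 requires a vaccination term in the primary model. It does not; it says only that vaccination is to be accounted for in the analyses. The case for the primary model is confounding.

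**Conclusion.** The point holds as a conditional one. Three things are certain from the text: the sentence in SAP 6.4.1 is wrong, the primary model has no calendar-time term, and no SAP analysis uses vaccination. The weighting that might have filled the gap is not in the SAP.

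Whether the hazard ratio will be biased is not known. It needs an association of prophylaxis use with local waves or with vaccination; without one the simulations gave 0.99-1.01. With one, the direction can go either way. The simulated size was about 0.90-1.12 for 15-point differences in use, 0.96-0.98 for 7 points, and 0.76-1.28 under the stronger assumptions.

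A reader might infer that the result will be biased towards benefit, or by a stated amount. The documents support neither. Nor do they show that facility strata are the only adequate repair: both calendar adjustments performed alike in the main scenarios. They parted only in an extreme case, with users' time zero 60 days later, where the SAP model gave 0.54, strata 0.98-0.99 and country-by-month 0.92.

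**What to change.** 1. Update the SAP to protocol v1.1.
2. Delete or correct the conditional-independence sentence in SAP 6.4.1.
3. Prespecify one calendar adjustment in the primary model, exempt from p-value selection: either facility plus country-by-calendar-month terms on the SAP clock, or calendar date as the time scale with delayed entry, stratified by facility. Report the other as a sensitivity analysis. If strata are primary, take the SAP 6.5 tests for facility and country from an unstratified model.
4. Force in time-varying vaccination status (unvaccinated, vaccinated, unknown) from the enrolment and weekly surveys, exempt from selection and correlation dropping. By default code time before the first vaccination answer as unknown. This includes time before enrolment, which matters because "at the time of enrollment, HCWs can be either SARS-CoV-2 positive (symptomatic or asymptomatic) or SARS-CoV-2 negative". Table 1 footnote c describes the weekly period as "Or, time since last follow-up, whichever is greater", so the SAP should also say whether a weekly no, without an enrolment answer, means unvaccinated or unknown.
5. Add two sensitivity analyses. One carries the first answer back: with VE 80% this gave 0.99-1.01, but with VE 0-20% and infected workers postponing vaccination by 180 days it gave 1.04, against 0.99-1.00 without carry-back. The other starts follow-up at the first answer. State that residual confounding remains in unknown person-time.

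**Cost.** SAP wording and programming; no new data. Facility strata raise the SE by 1-2% with 45 facilities, about 4% with 180 and about 12% with 540; the documents do not give the number. From 80% power, 4% gives Φ(2.802/1.04 − 1.960) = 77% and 12% gives Φ(2.802/1.12 − 1.960) = 71%. Vaccination status adds under 1%. The first-answer analysis keeps 60%, 46% or 30% of person-weeks if the questions go live on day 120, 200 or 280 (assumed), and its SE rises by 35%, 60% or 110%. It therefore suits a sensitivity analysis only.
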